Diagnosis and Main Inclusion Criteria	Heavy drinkers who self-identify as European-American and who have an average weekly ethanol consumption of ≥ 24 standard drinks for men or ≥ 18 standard drinks for women, with a weekly average of ≥ 2 heavy drinking days (HDDs) during the month before screening
Study Product, Dose, Route, Regimen	Topiramate 200 mg/day for 12 weeks. Dosage will be 200 mg/day, initiated at 25 mg/day and gradually increased such that the maximal dosage will be reached in the sixth week of treatment. The dosage will be altered to minimize adverse effects and after 12 weeks will be tapered off completely.
Duration of administration	12 weeks (plus a one-week taper)
Reference therapy	Placebo
Statistical Methodology	The four medication by genotype groups will be compared on weekly number of HDDs using mixed effects models for count responses. Estimates of effects over the final six weeks of treatment, with associated standard errors and confidence intervals, will be used to test the primary hypothesis. Similar models will be used to examine data from 3- and 6-month follow-up visits to evaluate the persistence of treatment effects. Regression analyses will also examine the effects of topiramate and rs2832407 and their interaction on resting baseline cerebral blood flow and alcohol cue reactivity.

CONFIDENTIAL

This material is the property of the University of Pennsylvania. Do not disclose or use except as authorized in writing by the study sponsor

1 Introduction

This document is a protocol for a human research study. The study is to be conducted according to US and international standards of Good Clinical Practice (FDA Title 21 part 312 and International Conference on Harmonization guidelines), applicable government regulations and institutional research policies and procedures.

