13.2 Risk/Benefits

Potential Risks

The potential risks of this study include the small risk incurred by venipuncture

Potential Benefits

Subjects will receive close psychiatric and medical attention, including careful evaluation of their medical and psychiatric status. The potential benefits to society include a potential improvement in the effectiveness of treatment for problem drinking, which may reduce the personal and societal costs associated with the problem.

Risk Benefit Ratio

The potential benefits of this study far outweigh the potential risks. Alcohol use disorders are serious disorders with mildly effective pharmacotherapy. Even in the best programs, relapse rates are high. Individuals accepted into this study will receive close medical and psychiatric monitoring. Subjects will be screened prior to admission into the study and those at risk for adverse reactions will be excluded.

14 Sub-Study Objectives

Objective 1: Demonstrate neuromodulatory effects of a GABA/glutamate modulator, topiramate, on RB and alcohol cue reactivity

CONFIDENTIAL

This material is the property of the University of Pennsylvania. Do not disclose or use except as authorized in writing by the study sponsor

Hypothesis 1: We hypothesize that topiramate will ameliorate neurophysiological vulnerabilities by dampening neural activity in the brain ‘at rest’ *and* during alcohol cue exposure in reward-related regions, such as the amygdala, mOFC, VS, and the insula. In contrast, neural activity in placebo-treated individuals at rest and in alcohol cue reactivity will not differ from pre- to post-treatment.

Objective 2: Examine the mechanism underlying topiramate’s ability to blunt alcohol cue reactivity and reduce heavy drinking days

Hypothesis 2: We hypothesize that there will be a direct relationship between RB in the VS and mOFC and its effects on alcohol cue reactivity. Although overall effects are expected, reductions in heavy drinking days will correlate with topiramate’s ability to modulate reward circuitry responses.

Exploratory Objective: Examine the moderating effects of rs2832407 on topiramate’s effects on brain and behavioral responses

Exploratory hypothesis: C-allele homozygotes at this locus will show the most robust effects of topiramate.

15 Sub-Study Design

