15.1 General Design

- **Phase II Study** - This is a phase 2 research study aimed at identifying the brain and behavioral mechanisms underlying the GABA/glutamate modulator, topiramate.
- **Design** – One hundred heavy drinkers who meet DSM-5 criteria for AUD and express an interest in reducing or stopping drinking will be recruited from the main study, screened, consented, and if eligible, receive 2 MRI scans. Scan 1 will occur before Topiramate or placebo is administered in the main study. Scan 2 will occur after subjects have received at least six weeks of medication in the main study (i.e., 6-8 weeks from the first dose of study medication). We will use perfusion and blood oxygen-level dependent (BOLD) fMRI during resting state and alcohol cue exposure to acquire brain and behavioral responses when the brain is “at rest” and during exposure to alcohol cues. The goals of this study are to pilot test the validity of our alcohol cues and to identify brain and behavioral mechanisms of topiramate in reducing heavy drinking in alcohol dependent individuals.

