17.2.2 Imaging Data Analyses

Global CBF time course will be included in the model as a covariate to examine the effects of topiramate on regional CBF. No temporal smoothing will be applied. Contrasts between conditions (alcohol cue vs non-alcohol cue; scan 1 vs scan 2) will be defined in the general linear model to assess the voxel by voxel CBF difference. Using the corresponding parametric maps of this contrast (β maps), random effects analysis will be employed to test for a significant main effect of condition with a statistical parametric map of the T statistic at each voxel for population inference for each session for the placebo and topiramate groups (second-level analysis). A 2x2 factorial design matrix will be used to assess the effects of the pharmacological manipulation by including the group (topiramate vs placebo) and condition (scan 1 vs scan 2) as the two factors. An associated contrast will be defined in this model to examine administration effects. This two-stage analysis is theoretically equivalent to a 2-way analysis of variance (ANOVA). Simple regression analyses will be conducted on CBF with the change in craving scores [post-alcohol cue minus pre-alcohol cue craving scores, number of heavy drinking days during the past 30 days, and age] as covariates of interest to test for prognostic brain/behavioral correlations. For the exploratory aim, subjects will be grouped by genotype (CC vs A-allele carrier) to examine the moderating effects of rs2832407 in *GRIK1* on topiramate effects using the same simple regression analyses described above. We will limit this analysis to European

CONFIDENTIAL

Americans, as that is the population in which the preliminary findings were obtained and allele frequencies differ significantly by population.

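### Section 17.2.2 states no model that tests the topiramate × rs2832407 interaction which the study summary promises for the imaging sub-study

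*Combined protocol and SAP*

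**What the plan says.** The Statistical Methodology entry of the Study Summary commits the sub-study to an interaction: "Regression analyses will also examine the effects of topiramate and rs2832407 and their interaction on resting baseline cerebral blood flow and alcohol cue reactivity".

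Section 17.2.2, Imaging Data Analyses, is where the models are set out. It has three relevant parts.

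- **Drug effect.** A 2×2 factorial model, "including the group (topiramate vs placebo) and condition (scan 1 vs scan 2) as the two factors".
- **Brain and behaviour correlations.** "Simple regression analyses will be conducted on CBF with the change in craving scores", with the number of recent heavy drinking days and age listed alongside as covariates of interest.
- **Genotype (exploratory aim).** The plan is that "subjects will be grouped by genotype (CC vs A-allele carrier"). The influence of the SNP is then to be assessed "on topiramate effects using the same simple regression analyses described above".

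The hypothesis behind the last part, in section 14, is that "C-allele homozygotes at this locus will show the most robust effects of topiramate". Section 14 calls this exploratory; section 15.3 lists the genotype effect as the sub-study's secondary endpoint. Section 15.1 sets the size: "One hundred heavy drinkers who meet DSM-5 criteria for AUD". Section 17.1 rests that number on previous research and gives no effect size, standard deviation or power.

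**The concern.** Moderation of a drug effect by genotype is a difference between two drug effects. Estimating it needs medication, genotype and their product in one model, or an equivalent contrast. The regressions that section 17.2.2 assigns to this question name no medication term, and the model that does contain medication has no genotype factor. The analysis stated for the aim therefore cannot answer it, although the summary says it will.

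The gap matters because an analyst has to fill it, and the easiest way is to look at the drug effect in each genotype separately. Sections 2.2 and 7.2 already phrase their genotype hypotheses as an effect present in C-allele homozygotes and absent in A-allele carriers, which makes that reading natural. Section 1.1.2 hopes that imaging will shed light on the mechanism of the pharmacogenetic effect. A chance pattern in the scans could then be cited in support of the main trial's hypothesis without any difference having been tested.

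**Working it through.** **Step 1: which terms each stated model contains.**

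| Source | Medication | Genotype | Medication × genotype |
|---|---|---|---|
| Study Summary | yes | yes | yes |
| 17.2.2, 2×2 factorial | yes | no | no |
| 17.2.2, simple regressions | not listed | no | no |
| 17.2.2, exploratory aim | not listed | by grouping | not listed |
| 7.2, main-trial primary model | yes | yes | yes |

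Grouping can mean separate fits by genotype or a genotype factor in one fit. Separate fits give a relation between CBF and craving, drinking or age in each genotype. A genotype factor gives a CBF difference between genotypes across both medication arms. Neither is a drug effect, so neither shows whether a drug effect differs.

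**Step 2: what could follow if the gap were filled by within-genotype drug tests.** The plan has no figure to reproduce here, so this is an illustration.

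Inputs: N = 100 (section 15.1); alpha 0.05 (section 17.2.3, stated for the behavioural analyses). Assumptions: two-sided tests; 25 subjects per medication × genotype cell (section 3.1 aims for comparable cells in the main trial only); one single test per genotype; the same true standardised effect d in both genotypes, so no moderation.

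Within-genotype power: p = Φ(d/√(2/25) − 1.96) + Φ(−d/√(2/25) − 1.96), with √(2/25) = 0.283.

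P(significant in exactly one genotype) = 2p(1 − p). The CC-only pattern is half of this, p(1 − p).

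Example, d = 0.5: 0.5/0.283 = 1.77, so p = 0.424 (the second term is negligible), and 2 × 0.424 × 0.576 = 0.488.

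| Common d | p | Exactly one genotype | CC only |
|---|---|---|---|
| 0 | 0.050 | 9.5% | 4.8% |
| 0.3 | 0.186 | 30% | 15% |
| 0.5 | 0.424 | 49% | 24% |
| 0.6 | 0.564 | 49% | 25% |
| 0.8 | 0.807 | 31% | 16% |
| 1.0 | 0.942 | 11% | 5% |

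Simulation with t-tests (20,000 replicates) gave 9.6%, 48% and 33% for exactly one genotype at d = 0, 0.5 and 0.8. A 43/57 genotype split, close to the 43.1% CC frequency in section 4.1.1, gives 9.5% to 50% over d = 0 to 0.8.

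**Step 3: the interaction test.** A common drug effect cancels in the difference of differences, so the false-positive rate does not depend on d. Simulation gave 5.1%, 5.1% and 5.0% at d = 0, 0.5 and 0.8.

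Its standard error is √(4/25) = 0.40 SD. For a difference of 0.66 SD, power is Φ(0.66/0.40 − 1.96) = Φ(−0.31) ≈ 38%. The 0.66 is 0.93 − 0.27 from section 7.1, which concerns drinking; using it for CBF is an assumption.

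**The case against.** Three arguments can be made for the plan as it stands.

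**It sets no faulty decision rule.** A reader might infer that moderation will be declared by comparing significance in one genotype with non-significance in the other, in place of an interaction test. The text does not say so. It gives no rule for declaring moderation and does not exclude an interaction term. This stands: the defect is an omission and a mismatch with the summary, not a rejection of the right test.

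**The error rates belong to a procedure that is not in the text.** The rates in the table need drug-versus-placebo tests within each genotype, and the listed regressions contain no such tests. A reader might take 30% to 50% as the plan's false-claim rate. That is not supported: the rates are conditional on how the gap is filled, they fall to about 10% at both ends of the range shown, and the plan supplies no effect size to place it on that range. Section 17.2.2 also works voxel by voxel, so a single test at 0.05 is only a rough analogue. All of this stands.

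**The summary and section 17.2.2 can be read together, and the aim is exploratory.** On this view the summary names the target and section 17.2.2 is merely brief. This stands only in part. Section 17.2.2 does not leave the model open: it points to particular regressions, and those lack medication. The exploratory label does lower the stakes, although section 15.3 gives the same question a higher status.

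**Conclusion.** The point holds as an internal inconsistency with a practical consequence. Followed exactly, section 17.2.2 contains no model that tests whether the topiramate effect on resting CBF or cue reactivity differs by rs2832407 genotype, and the Study Summary says such an analysis will be done. This conclusion comes from the text and needs no numerical assumption.

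The size of the possible harm is conditional. If within-genotype significance were compared, false moderation patterns would arise in roughly 10% to 50% of cases with no true moderation, against 5% for the interaction test. That rests on 25 per cell, two-sided alpha 0.05, a single test per genotype, and a common d between 0 and 1.0.

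A reader might also infer that the main trial's genotype result is at risk. It is not: the primary model in section 7.2 includes medication, genotype and their interaction, and the sub-study has no part in that test.

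**What to change.** In section 17.2.2, replace the sentence on the exploratory aim with a model that carries the interaction. Extend the existing second-level model from group × scan to group × scan × genotype. Equivalently, model the scan 2 minus scan 1 change on medication, genotype and medication × genotype. Apply it both to resting CBF and to the alcohol versus non-alcohol cue contrast, since the summary names both. The planned voxel-wise framework can stay.

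Then add three statements:

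- any claim of moderation rests on the interaction estimate and its confidence interval;
- results within each genotype are descriptive;
- power for the interaction is low at N = 100, about 38% for a 0.66 SD difference under the assumptions above.

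The simple regressions can remain for the brain and behaviour correlations they were written for. The change needs no new data, visits or subjects, and it brings the section into line with the Study Summary and the main-trial model in section 7.2. The only cost is stating openly that the exploratory analysis may well be inconclusive.

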17.2.3 Behavioral Analyses

Statistical significance tests use an alpha of .05 unless otherwise noted. Continuous demographic variables (e.g., age, education, quantity/frequency of alcohol use) are checked for normality, transformed if necessary, and summarized by calculating means, standard deviations and ranges. Scores on each factor will be included as covariates of interest with respect to perfusion fMRI data and genetic variance. Analysis of variance will be used to assess demographic differences across groups. Nominal demographic variables (e.g., race, sex, genotype) are summarized by calculating proportions and compared across groups using chi square analyses. Demographic (age, years education, monthly income) and clinical (depression, anxiety) will also be summarized.

17.3 Subject Stipends or Payments

Subjects will be paid \$50 to complete the Screening and Informed Consent visit. They will also be paid \$150 to complete the initial MRI session visit, and \$200 to complete the second MRI visit. The total amount that subjects can receive for full participation in the sub-study is \$400. Payments will be made with a GreenPhire ClinCard. Clincards are reloadable prepaid cards that may be used for in-store purchases (by selecting either the “credit” or “debit” option), online purchases, at an ATM to get cash, or for cash advances at a bank.

Schedule for Sub-Study Payments

Visit	Payment	Total
Screening and Informed Consent	\$50	\$50
MRI Scanning Visit 1	\$150	\$150
MRI Scanning Visit 2	\$200	\$200
Totals	Up to \$400	\$400

*Subjects will receive a pro-rated portion of the payment based on the extent to which they complete the study visit.

***ALL REMAINING ASPECTS OF THE SUB-STUDY ARE DESCRIBED ABOVE IN SECTIONS 8-12.**

18 Confidentiality

A Certificate of Confidentiality from the National Institute on Alcohol Abuse and Alcoholism (NIAAA) that is separate from the one for the main study will be obtained for the sub-study described in this protocol. As per the NIAAA's website: Confidentiality Certificates are issued by NIH Institutes pursuant to Section 301 (d) of the Public Health Service U.S.C. Section 241 (d) to afford special privacy protection to subjects enrolled in biomedical, behavioral, clinical, or other research within NIH mission areas. A Certificate helps the researcher avoid compelled 'involuntary disclosure' (e.g., subpoenas) of identifying information about a research subject. It does not prevent voluntary disclosures such as disclosure to protect the subject or others from serious harm, as in cases of child abuse. Also, a researcher may not rely on a Certificate to withhold data if the subject consents to the disclosure. When a researcher obtains a Certificate of Confidentiality, the subjects must be told about the protections afforded by the Certificate, and any exceptions to that protection. This information is usually included in an 'informed consent'.

CONFIDENTIAL

This material is the property of the University of Pennsylvania. Do not disclose or use except as authorized in writing by the study sponsor

All subjects will be informed about the protections afforded by the Certificate in the Informed Consent Form for both the main and sub-study using the language inserted below:

“To further help us protect your privacy, we have obtained a Certificate of Confidentiality from the United States Department of Health and Human Services (DHHS).

With this Certificate, we cannot be forced (for example by court order or subpoena) to disclose information that may identify you in any federal, state, local, civil, criminal, legislative, administrative, or other proceedings. The researchers will use the Certificate to resist any demands for information that would identify you, except to prevent serious harm to you or others, and as explained below.

You should understand that a Certificate of Confidentiality does not prevent you, or a member of your family, from voluntarily releasing information about yourself, or your involvement in this study.

If an insurer or employer learns about your participation, and obtains your consent to receive research information, then we may not use the Certificate of Confidentiality to withhold this information. This means that you and your family must also actively protect your own privacy.

You should understand that we will in all cases, take the necessary action, including reporting to authorities, to prevent serious harm to yourself, children, or others (for example, in the case of child abuse or neglect).”

This language is located in the section of both of the Informed Consent Forms titled “Who can see or use my information? How will my personal information be protected?”

19 APPENDIX II: CLINCARD PROGRAM: DATA SECURITY & PRIVACY STATEMENT

ClinCard Program: Data Security & Privacy Statement

Updated 14 January 2016

Confidentiality of Protected Health Information (PHI)

All clinical trial participant information is stored securely. Greenphire does not sell, use or distribute clinical trial participant information for any purpose other than those needed to execute, service and maintain the ClinCard program (including ClinCard Direct Deposit and Travel Reimbursement methods). Greenphire protects the privacy of Electronic Protected Health Information (“EPHI”), disclosed or provided to us in compliance with the Security Standards for the Protection of Electronic Protected Health Information at 45 CFR Sections 160 and 164 (the “Security Rules”). Towards that end, Greenphire has implemented administrative, physical, and technical safeguards (detailed below) that reasonably and appropriately protect the confidentiality, integrity, and availability of EPHI; ensures that any agent or subcontractor to whom we provide EPHI agrees to implement reasonable and appropriate safeguards to protect it; and will report any Security Incident involving EPHI of which it becomes aware within five (5) days of learning of the Security Incident.

Data Information Security

As a matter of policy and commitment to clients and clinical trial participants, Greenphire takes great strides to protect all information relating to cardholders. Greenphire has deliberately designed its payments and communication platform including all of Greenphire’s externally facing web tools to actively protect all data transfers and data stored with Greenphire’s infrastructure:

Database and Encryption– All passwords within our database are protected using the one-way SHA1 algorithm to encrypt passwords, which are then encrypted by the one-way MD5 algorithm. Where

CONFIDENTIAL

This material is the property of the University of Pennsylvania. Do not disclose or use except as authorized in writing by the study sponsor

necessary, Greenphire's platform makes use of encryption using the 256 bit Advanced Encryption Standard (AES or otherwise known as Rijndael), which is one of the most popular algorithms used in symmetric key cryptography. AES is approved by the US National Intelligence Agency (NSA) for top secret information.

Web Tools – All of Greenphire's web tools that are involved in transferring data between an end-user's web browser and Greenphire's platform (and vice versa) are secured by 256 bit Secured Socket Layer (SSL) with TLS 1.2 encryption. Greenphire is able to track the activities performed on accounts by site administrators through a system of unique logins which allow users access to the clincard.com web tool. In addition, all user activities in the Greenphire Platform are auditable.

Financial Data Transfer - Communications between the Greenphire platform and financial networks are executed via Web Service (API) or sFTP transport.

Physical Protection – Greenphire houses its internal database on servers that are located in a highly secure, off-site facility. Access to the physical servers at the facility is limited to Network Operations Center (NOC) Engineers and Technicians. The facility is secured with a bio-metric security system that can track access to the facility and is monitored by digital security video surveillance, includes multiple suppliers for network connectivity and redundant power supplies including on-site power generation in the event of emergency.

Authorized Access – Greenphire restricts access to sensitive data to only a limited number of essential internal personnel. Authorized individuals are only permitted to access data if it is required to service our client, their authorized users or the clinical trial participant. The number of authorized individuals remains limited to protect against internal threats to the security of sensitive data.

Proactive Design - Greenphire's internal technology platform has been intentionally designed to exclude the requirement of certain sensitive information that other similar companies require to be stored in their systems, such as PIN numbers. If new types of sensitive data must be introduced and stored, per the design of a specific protocol, Greenphire will protect the data using the encryption methods described previously.

